10.4.2 ANALYSIS OF THE PRIMARY EFFICACY ENDPOINT(S)

Data for the primary efficacy endpoints will be tested to determine if they are parametric. For parametric data the differences between the baseline and subsequent visits will be tested using a Student's t-test. Non-parametric data may be tested using the Mann Whitney U test. Additional statistical methods may be utilized if required. Any deivations from the previously approved statistical plan will be described and justified in a protocol amendment and/or in the final report submitted to this application.

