10 STATISTICAL CONSIDERATIONS

10.1 STATISTICAL AND ANALYTICAL PLANS

All statistical analyses will be performed in conjunction with the consultant biostatistician([name]). The proposed sample size of 20 subjects for the Phase II expansion cohort was determined to detect, with an 80% power at a 5% type-1 error rate, a change of 15.9 points on the primary endpoint (ie. SNOT-22 score) between baseline and 4 weeks. This calculation was based on two assumptions. The first is a target effect size of 15.9 which represents a conservative value derived from the established MCID for the SNOT-22 of 8.9[65] and the LSM change in SNOT-22 of 27.7 derived from our previous trial of oral Verapamil(Section R.4.d)[19]. The second is an anticipated standard deviation of 24 which is calculated from the standard deviations of 30 both at the baseline and 8 week time point observed in our oral Verapamil trial and an r2 of 50% between the two time points. With a significance level of 0.05, a standard deviation of 24, and 80% power, a sample size of 20 would be needed to detect a difference of 15.9. Analysis of efficacy will be based on an intention-to-treat population that will include all enrolled patients. A mixed-effect model with repeated measures approach will be used to independently analyze the change in the SNOT-22, VAS, and LKS. An intraclass correlation coefficient (ICC) will be calculated to assess inter-rater agreement with respect to the LKS scores. Descriptive statistics will be used for demographics, baseline characteristics, and safety variables. Linear regression models will be fitted to examine the interaction effect between baseline characteristics, whole mucus and exosomal P-gp concentrations, mucus and irrigant cytokine concentrations, and treatment on change in SNOT-22 while adjusting for the baseline SNOT-22 score. Statistical analyses will be performed using the statistical software SAS (SAS Institute Inc., Cary, NC)

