10.5 SAMPLE SIZE

The sample size for the Phase II arm was determined in consultation with [name] (biostatistician). It is based on the MCID for the SNOT-22 and the least suare means value for the SNOT-22 that was determined by the previous oral verapamil trial conducted by [name]. The new, combined MCID for the SNOT-22 was determined to be 15.9. The standard deviation for this trial is 24. This was calculated using the standard deviation of the oral verapamil trial (30) and an r^2 of 50%. With a significance level of 0.05, a standard deviation of 24, and 80% power, a sample size of 20 is needed to detect a difference of 15.9.

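### Section 10.4.2 names an independent-samples rank test (Mann-Whitney U) as the optional fallback for one group of 20 patients measured before and after treatment, and does not rank its tests against the mixed model in section 10.1.

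*Combined protocol and SAP*

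**What the plan says.** Phase II is a single open-label cohort of 20 (section 4.1), with no randomization (section 10.6.1). SNOT-22 is taken at baseline, day 7 and day 28 (section 7.3.7). The null hypothesis in section 10.2 compares baseline with week 4, and section 10.1 sizes the trial for "a change of 15.9 points on the primary endpoint (ie. SNOT-22 score) between baseline and 4 weeks".

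Section 10.4.2 opens: "Data for the primary efficacy endpoints will be tested to determine if they are parametric". It continues: "For parametric data the differences between the baseline and subsequent visits will be tested using a" Student's t-test. Then: "Non-parametric data may be tested using the Mann Whitney U test", followed by "Additional statistical methods may be utilized if required". Departures from the plan are to be described and justified. Section 10.4.3 carries the same methods to the secondary endpoints, so VAS and LKS inherit them.

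Section 10.1 separately says: "A mixed-effect model with repeated measures approach will be used to independently analyze the change in the SNOT-22, VAS, and LKS". It bases the sample size on "an anticipated standard deviation of 24 which is calculated from the standard deviations of 30 both at the baseline and 8 week time point", together with an r² of 50%. Section 10.5 repeats the result: "With a significance level of 0.05, a standard deviation of 24, and 80% power, a sample size of 20 is needed".

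**The concern.** Mann-Whitney U is a test for two independent samples, and Phase II has none. Using it would treat the 20 baseline scores and the 20 week-4 scores as if they came from 40 different people. It would discard the within-patient correlation on which the sample size rests. The stake is a missed effect on the primary endpoint, in a trial with only 80% planned power.

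Three gaps widen the problem. The t-test is not called paired. The normality check is not named, and the text does not say whether it applies to the within-patient differences or to each visit's scores. The mixed model in 10.1 and the tests in 10.4.2 are both planned for SNOT-22, and neither is designated primary.

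**Working it through.** **Inputs.** From sections 10.1 and 10.5: n=20, change 15.9, SD 30 at each time point, r² 50%, SD 24, 5% significance, 80% power. From section 5.1: Phase II baseline SNOT-22 of at least 30. Sidedness is not stated.

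**1. What SD 24 is.** SD of change = √(2 × 30² × (1 − r)). With r = √0.5 = 0.707 this is 22.96. SD 24 corresponds to r = 1 − 576/1800 = 0.68. So 24 is an SD of within-patient change, and r between 0.68 and 0.707 is used below.

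**2. Reproducing n=20.** Paired t-test, noncentrality = (15.9/24) × √20 = 2.96, 19 df.
- Two-sided 5%: power 80.2% at n=20 and 78.0% at n=19, an exact match. With SD 22.96 the power at n=20 is 83.6%.
- One-sided 5%: only 16 patients would be needed, so two-sided is taken as intended.
- Two independent groups, two-sided: 37 per group (SD 24) or 57 per group (SD 30). With 20 per group, power is 53% or 37%.
- Two independent groups, one-sided: 29 or 45 per group.

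No independent-samples version gives 20.

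**3. What ignoring the pairing does.** An unpaired comparison uses a standard error of about √(2 × 900/20) = 9.49. The true standard error of the mean change is 24/√20 = 5.37. Significance then needs an observed change of roughly 1.96 × 9.49 = 18.6 points, more than the 15.9 planned for.

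**4. Simulated rejection rates** (100,000 trials per cell, normal data, two-sided 5%, r = 0.68 / 0.707):

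| Test | Change 15.9 | No change |
|---|---|---|
| Paired t | 80.1% / 83.6% | 5.0% / 5.1% |
| Signed-rank | 77.9% / 81.7% | 4.9% / 4.9% |
| Mann-Whitney | 28.7% / 28.3% | 0.18% / 0.12% |

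**5. With the entry cut-off.** Assume that SD 30 and r describe patients before the SNOT-22 cut-off, with population means of 40 to 60 and a mean change of 15.9 among those enrolled. The documents give none of these assumptions. At r=0.68, Mann-Whitney power is 41-53% against 83-84% for paired t. Taking in r=0.707 as well, the ranges are 41-55% against 83-87%.

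**6. Section 10.4.2 as a whole** (t-test run paired; Shapiro-Wilk at 5% is my assumption; shared-gamma skewness; 5,000 trials; r = 0.68 / 0.707):

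| Scores | Paired t alone | Differences checked | Each visit's scores checked |
|---|---|---|---|
| Normal | 79.1 / 82.5% | 76.6 / 79.9% | 75.0 / 78.0% |
| Skewness 1 | 80.5 / 83.5% | 73.7 / 75.2% | 63.0 / 65.9% |
| Skewness 2 | 81.9 / 83.4% | 76.3 / 76.8% | 71.8 / 72.4% |

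The loss runs from 79.1 − 76.6 = 2.5 points to 83.5 − 65.9 = 17.6 points. A repeat of the simulation gave about 3-7 points (differences checked) and 5-16 (scores checked). With normal data and differences checked, the fallback is reached in 5% of trials.

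**7. Unranked analyses.** Taking the smallest p of paired t, mixed-model contrast and Mann-Whitney gives a type I error of 6.0-6.1%.

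**8. Limits of signed-rank.** With mean-zero gamma-distributed changes at n=20, signed-rank rejects in about 7% (skewness 1), 9% (skewness 1.5) and 13% (skewness 2). Paired t rejects in about 6%, 7% and 8%. The skewed models in step 6 have symmetric differences, so they do not show this.

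**The case against.** The defect is one optional fallback. Section 10.4.2 permits Mann-Whitney rather than requiring it, allows other methods, and asks for departures to be justified. Section 10.1 commits to a repeated-measures model, which respects the pairing whichever way a normality check falls. The t-test on differences from baseline reads naturally as paired. All of this stands, and it limits the severity.

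It does not remove the point. The only rank test named is the wrong one. Choosing the right one after seeing the data is not pre-specification. The section headed as the primary-endpoint analysis does not mention the mixed model.

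A reader might infer that the primary analysis has only 28-29% power. The documents do not support that. The figure is for normal data, where 10.4.2 prescribes the t-test, and it rises once the entry cut-off is considered. A reader might also infer that 10.1 and 10.4.2 contradict each other. They are compatible; what is missing is an order between them.

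It is also fair to object that signed-rank is not a free repair. Section 10.2 states the null in terms of means, and signed-rank can be liberal for that null when changes are skewed. The fix has to say so.

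**Conclusion.** Wrong as written, and should be fixed, but not a flaw that undermines the trial. The named fallback does not match the design or the basis of the sample size. Its error is conservative, so it does not raise the false-positive rate; the cost is power. Where it is used, power falls well below that of a paired test. Over 10.4.2 as a whole the loss is roughly 3 to 18 points, and the upper end needs skewed data with normality checked on each visit's scores.

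The sample size of 20 is not in question: it is right for a two-sided paired t-test, and signed-rank comes close (about 78%). The missing ranking matters less, at about 6% type I error instead of 5%, and only if someone picks the smallest p-value.

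These sizes rest on the plan's SD and correlation, on two-sided 5%, on complete data, and on assumed forms for skewness, the normality check and the truncated baseline. That Mann-Whitney ignores the pairing depends on none of them.

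**What to change.** - Name one primary within-patient analysis of the baseline to week-4 SNOT-22 change, at two-sided 5%: either the mixed-model contrast of section 10.1 or a paired t-test. Make the other a sensitivity analysis.
- In section 10.4.2, write paired before t-test.
- Replace Mann-Whitney U with the Wilcoxon signed-rank test on within-patient differences, as the fallback or a sensitivity test. Note that it assumes symmetric differences and can be liberal for a mean-zero null when changes are skewed. If the mixed model is primary, signed-rank serves as sensitivity only.
- If a normality check is kept, name it and apply it to the within-patient differences.
- Apply the same to VAS and LKS through section 10.4.3.

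The cost is protocol and SAP wording only, with no new patients, visits or data.

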10.4.3 ANALYSIS OF THE SECONDARY ENDPOINT(S)

Data for the secondary endpoints will be analyzed using the same methods as the primary endpoints.

10.4.4 SAFETY ANALYSES

The safety of the drug will be determined by analyzing the rate of adverse events in both phases of the trial. An occurance of 10% within the study population will be considered significant.

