> dose step design. Participants will administer each dose Verapamil HCl dose intranasally BID. Weekly visits will occur for side-effect and escalation evaluations. Phase II will be an open label trial of 20 participants. The MTD determined in Phase Ib will be administered BID for 4 weeks.

Participants will be seen at baseline, 1 week, and 4 week for efficacy and side-effect

evaluations.

Objectives: Primary Objectives:

> -Perform a Phase IB trial of topical intranasal Verapamil HCl BID to determine the Maximal Tolerated Dose(MTD) using an accelerated titration design with intra-patient dose escalation. -Perform a Phase II trial of topical intranasal Verapamil HCl BID based on the Phase I MTD to determine safety and efficacy using both subjective and objective outcome measures of CRS. Secondary Objective:

-Determine whether mucus derived exosomal P-gp can be used as a non-invasive biomarker of CRS by correlating it with baseline symptoms of CRSwNP and treatment response to topical

Verapamil HCl at the MTD. **Endpoint**

Primary Endpoints:

Phase Ib: Defining the Maximal Tolerated Dose(MTD) of topical Verapamil HCl. DLT will be defined as a development of 2nd or 3rd degree heart block as measured by an EKG.

Phase II: determining the efficacy of topical Verapamil HCl at the MTD for subjective symptoms

of CRSwNP using the validated SNOT-22.

Secondary Endpoints:

Phase Ib: Intermediate toxicity will be defined as: a heart rate of <50, an asymptomatic BP reduction >30% from baseline or SBP <90mmHg, an asymptomatic AMP reduction >30% from baseline or MAP<55, an asymptomatic DBP reduction >30% from baseline, and a Meltzer Compliance Grade >4.

Phase II: to determine the efficacy of Verapamil HCl at the MTD as measured by a subjective 10cm visual analog scale(VAS), Meltzer topical irrigation satisfaction and compliance scores, and the validated Lund-Kennedy nasal endoscopy score(LKS).

Population: 20-40 MEE Sinus Center patients over the age of 18 who present with chronic

rhinosinusitis with polyps.

Phase: IB/II
Number of 1

Sites enrolling participants:

Description Verapamil HCl 0.3mg-3.6mg final dose BID in buffered normal saline as a nasal

of Study irrigation.

Agent:

[figure not shown]
Study December 2016 – December 2018

Duration:

[figure not shown]
Participant 1 month

Duration:

SCHEMATIC OF STUDY DESIGN

Legend				
IC	Informed Consent			
IF	Intake Form			
PT	Pregnancy Test			
SNOT-22	Sino-Nasal Outcome Test			
VAS	Visual Analogue Scale			

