2.3 POTENTIAL RISKS AND BENEFITS

2.3.1 KNOWN POTENTIAL RISKS

Verapamil HCl is a cardioactive drug and thus there is a theoretical risk of cardiac side effects from the medication. This will be mitigated by obtaining a EKG which will be reviewed by a medical internist/anesthesiologist prior to initiating therapy. Follow-up EKGs will also be performed to monitor for cardiac side effects. The risk of cardiac effects appears to be dose-dependant and is expected to be mostly reversible upon discontinuation of the drug. Additional risks include bradycardia and hypotension. These will be mitigated by checking routine vital signs at each visit which will include heart rate and blood pressure. Constipation is also a risk of the drug. This will be asked about at each visit and stool softeners and/or laxatives will be administered as necessary. Since verapamil will be administered with a nasal rinse there is a possibility of nasal irritation. These side effects will be monitored at each study visit.

There are currently few medical interventions available for CRSwNP. The development of new medications is critical to the management of this disease. Thus, the short-term risks for the trial patients will ultimately decrease the risks and discomforts that the overall CRSwNP population experiences.

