The Phase II study will be an open label safety and efficacy expansion cohort using the MTD determined in the Phase IB arm. A total of 20 patients will be administered the MTD of topical Verapamil HCl in a 240mL buffered normal nasal rinse for 4 weeks BID. This sample size was calculated based on a power analysis derived from the results of our oral Verapamil trial. The first dose will be administered in in a 10th or 11th floor MEE clinic withhemodynamic monitoring. A medically trained member of the study staff with monitor the patient for one hour. Patients will be instructed on the how to properly perform the irrigation using a pre-recorded video demonstration. If no first-course DLT occurs then patients will continue taking the topical Verapamil dose BID. Patients will then return for follow-up visits at 1 week and 4 weeks. Subjective and objective outcome measures will be collected at each visit.

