4.2.1 PRIMARY ENDPOINT

Phase Ib:

The primary outcome measurement for Phase IB(SA1) will be defining the Maximal Tolerated Dose(MTD) of topical Verapamil HCl. Dose Limiting Toxicity will be defined as a development of 2nd or 3rd degree heart block as measured by an EKG.

Phase II:

The primary outcome for Phase II(SA2) will be determining the efficacy of topical Verapamil HCl at the MTD for subjective symptoms of CRSwNP using the validated SNOT-22.

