8.1.1 DEFINITION OF ADVERSE EVENTS (AE)

An adverse event will be defined as any untoward medical occurrence associated with the use of intranasal Verapamil HCl, whether or not it is considered related to the intervention.

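### Section 10.4.4 judges drug safety by a raw 10% adverse event rate that does not separate heart block from mild or unrelated events and carries no confidence interval

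*Combined protocol and SAP*

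**What the plan says.** Section 10.4.4 is two sentences long. The first reads "The safety of the drug will be determined by analyzing the rate of adverse events in both phases of the trial" and the second "An occurance of 10% within the study population will be considered significant". Nothing follows about event class, counting unit, denominator, test, interval or consequence.

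The surrounding text matters in four ways:

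- **What counts.** Section 8.1.1 defines an AE as "any untoward medical occurrence associated with the use of intranasal Verapamil HCl, whether or not it is considered related to the intervention". Mild and unrelated events are therefore included. Section 2.3.1 names minor effects that could occur: nasal irritation as a possibility, and "Constipation is also a risk of the drug".
- **The event of most concern.** Section 4.2.1 states "Dose Limiting Toxicity will be defined as a development of 2nd or 3rd degree heart block as measured by an EKG". Section 10.4.4 does not mention it.
- **Denominator.** Section 4.1 says "A total of 20 patients will be administered the MTD of topical Verapamil HCl". The Protocol Summary gives the whole study as "20-40 MEE Sinus Center patients over the age of 18". Section 5.4 replaces withdrawn participants.
- **Presentation.** Section 10.1 plans descriptive statistics for safety variables, and section 10.4.1 plans means and standard deviations. Neither plans an interval for a proportion.

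Other thresholds appear elsewhere: an AE rate of 20% in sections 5.5 (above it) and 8.5 (on reaching it), and severe AEs in 20% of the population in section 10.4.7.1. Those concern suspension or halting.

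**The concern.** Section 3 makes safety at the maximal tolerated dose part of a primary objective for Phase II, and section 10.4.4 is the only rule that turns the safety data into a conclusion. A single percentage over all AEs weighs events by count alone. Two brief, unrelated complaints can outweigh one heart block. A result on the favourable side of the line may also be read as evidence of a low rate, which 20 participants cannot provide at the usual confidence levels. The likely harm is a misleading safety statement in the final report, in either direction.

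**Working it through.** **Inputs.** Threshold 10% (10.4.4); Phase II n = 20 (4.1); AE definition (8.1.1); DLT definition (4.2.1). The true event rates below are assumptions, because the documents give none.

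**The plan's own n.** Section 10.1 says "With a significance level of 0.05, a standard deviation of 24, and 80% power, a sample size of 20 would be needed" to detect 15.9 SNOT-22 points. A paired t-test (noncentral t, two-sided 0.05; the plan does not state sidedness) has noncentrality (15.9/24) × √20 = 2.96. Power is 80.2% at n = 20 and 78.0% at n = 19. The 20 reproduces, but it was sized for SNOT-22 and not for an AE rate.

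**Step 1: reaching 10%.** Read the rule as participants with any AE, at or above 10%, in 20. Since 2/20 = 10.0%, two participants suffice. P(X ≥ 2) = 1 − (1−p)^20 − 20p(1−p)^19:

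- p = 5%: 26%
- p = 10%: 61%
- p = 20%: 93%

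**Step 2: one heart block.** 1/20 = 5.0%, below the line, with an exact 95% interval of 0.1% to 24.9%. At an assumed true risk of 5%:

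- P(exactly one case) = 20 × 0.05 × 0.95^19 = 37.7%
- P(no case) = 0.95^20 = 35.8%

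Only the 37.7% bears on the criterion, because no rule can flag an event that did not occur.

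**Step 3: falling below 10%.** With no events in n, the exact upper bound is 1 − α^(1/n). At n = 20:

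- one-sided 95%: 1 − 0.05^(1/20) = 13.9%
- two-sided 95%: 1 − 0.025^(1/20) = 16.8%

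If the true rate is 10%, no events in 20 still occurs with probability 0.9^20 = 12.2%. To bring the bound under 10% with no events needs ln(0.05)/ln(0.9) = 28.4, so n = 29 (one-sided), or ln(0.025)/ln(0.9) = 35.01, so n = 36 (two-sided).

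**Step 4: other readings.**

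- *Strictly more than 10%:* three of 20 are needed; P(X ≥ 3) is 7.5%, 32% and 79% at 5%, 10% and 20%.
- *21 treated after a replacement:* 2/21 = 9.5%, so two participants fall short.
- *Phases pooled, up to 40:* the line moves to 4/40, and 0/40 gives upper bounds of 7.2% (one-sided) and 8.8% (two-sided).
- *Per event type:* two participants need the same type of event; one heart block is still 5%.
- *Lower confidence:* the one-sided bound for 0/20 is 10.9% at 90% and 7.7% at 80%, so Step 3 fails at 80%.

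**The case against.** The strongest reply is that section 10.4.4 is terse rather than wrong. It does not say that an event under 10% is unimportant, nor does it promise to demonstrate a rate under 10%. The figures above follow from one reading among several. Severity and relatedness are already recorded under section 8.3, and individual reporting is already required under section 8.4. Much of this stands, and it is why the figures are conditional. It does not rescue the criterion: the section says safety is determined from this rate and gives no other basis.

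Three stronger inferences are tempting and not supported:

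- **That a heart block would be overlooked.** Continued Phase II dosing depends on no first-course DLT (4.1), all AEs go to the IRB and DSMB (8.4.1), and the EKGs are reviewed medically and the safety data by the DSMB (9). The gap is only in the final safety criterion.
- **That about 74% of trials would miss a 5% heart-block risk because of this rule.** That sum (35.8% + 37.7%) includes the trials with no case, which no criterion could flag.
- **That one AE of any kind meets the criterion in Phase Ib.** This needs 10 or fewer participants. The documents fix no Phase Ib size: the study total of 20-40 leaves up to 20 beyond Phase II, and section 9 schedules DSMB review after 3 participants and then every 6.

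Nor do the documents give a background AE rate, so it cannot be said that minor events would usually trip the rule.

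**Conclusion.** The point holds in conditional form. As written, the criterion for part of a primary objective treats all AEs alike and ignores sampling error. It rests on participants with any AE being counted in Phase II alone, exactly 20 treated, and 10% inclusive. On that reading, two participants with mild or unrelated AEs meet it, while a single DLT at 5% does not meet it on its own. At an assumed 5% heart-block risk, 37.7% of trials would have exactly one case, to which the criterion gives no separate status.

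A reader might infer from a rate under 10% that the true rate is under 10%. Even 0/20 does not support that at one-sided 90% or 95%, or at two-sided 95%, with exact limits. The numbers shift under the other readings, and the plan does not say which reading applies. This should be changed; it does not invalidate the trial.

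**What to change.** 1. Delete the 10% criterion from section 10.4.4 as the basis for the safety conclusion.
2. Report every DLT and every serious AE individually, whatever its percentage.
3. For other AEs, report the number and percentage of treated participants by term, severity and relatedness, separately by phase, with exact (Clopper-Pearson) 95% confidence intervals. These replace the means and standard deviations of section 10.4.1 for event data. State that the unit is the participant and the denominator is everyone treated, including those later replaced.
4. Make no claim that a rate is below a limit unless the exact upper bound is below it. At n = 20 the one-sided 95% bounds are 13.9% for 0 events, 21.6% for 1 and 28.3% for 2.
5. Reconcile the 10% figure with the 20% AE rate in sections 5.5 and 8.5 and the 20% severe AE figure in section 10.4.7.1, so that each has a stated purpose. Which halting threshold should apply is for the sponsor and the DSMB.

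The cost is a rewritten section and a few extra tables. Section 8.3 already collects severity and relatedness, so no new data or participants are needed. The safety statement becomes weaker, but it will be one that 20 participants can support.
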